4.1 TREATMENT ASSIGNMENT PROCEDURES

Each participant will experience two experimental conditions (glucose drink and water). There are 2 ways to order the two conditions (glucose drink and then water, water and then glucose drink). By randomization, each participant will be assigned to one of the sequences. Ten participants will be assigned to each of these 2 sequence groups. Each session has at least a 3-day gap to minimize the presence of outlasting effects of either the GTT or the TMS. The randomization schedule will be computed prior to recruitment of subjects and the random assignments will be concealed from the personnel who screen potential participants until the moment that the participant is enrolled and ready for baseline evaluations. To accomplish this, the randomization schedule will be used to create a set of sequentially-numbered opaque sealed envelopes.

- Glucose drink → Drinking water (10 participants)
- Drinking water → Glucose drink (10 participants)

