4 BASIC STUDY DESIGN

Participants who pass an initial screening by phone are asked to attend a screening visit where consent is provided, eligibility for study participation is confirmed and demographic information is collected. Participants who are eligible to participate will then be asked to return for two study sessions after an MRI scan. Sessions will start at 8.00 am and study participants will be asked to fast for the preceding 12 hours and to consume approximately 150g of carbohydrates each day for the 3 days prior to the session. The study procedures are identical for both study visits. The order of the two sessions is equally randomized across participants.

In one visit, an oral 3-hour GTT with a 75g load of glucose will be administered. In the other visit, pure drinking water will be used. Both study visits have the following time-line:

1. Determined the target (hand area of the left precentral gyrus, left primary motor cortex) based on MR images using a TMS neuro-navigation system.
2. Fitting of an EEG electrode net.
3. Baseline EEG and MEP measurements elicited by TMS
4. Measurement of fasting blood glucose level by finger prick
5. Administration of drink (glucose drink or water, 296mL of H₂O for both drinks)
6. Capillary blood draw (finger prick) for glucose level testing and TMS-induced EEG and MEP measurements at 0, 30, 60, 120, 180 minutes after drink administration
7. Digitization of EEG electrodes on the scalp using a camera-type scanner

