Single-pulse TMS on the motor cortex leads to a twitch in the target muscle evoking a motor-evoked potential (MEP) measured by electromyography (EMG) electrodes. Participants will be seated in a comfortable armchair with their hands positioned on the armrest. Two disposable electrodes (15x21mm, Ambu Neuroline) will be placed in a tendon-belly arrangement over the first dorsal interosseous muscle and a ground electrode will be placed over the styloid process of the ulna. A figure-eight coil (C-B60, MagVenture) will be used for stimulation and EMG signals will be recorded by an amplifier (MagPro X100, MagVenture). The coil will be placed tangentially over the scalp with the handle pointing backwards and laterally at 45° from the mid-sagittal line. Biphasic TMS pulses will be applied over the motor cortex and the resting motor threshold (RMT) will be defined by the minimum TMS intensity required to evoke MEP of at least 50 uV in 50% of 10 consecutive trials. At baseline, 10 TMS pulses will be applied on the scalp and EEG and EMG data will be collected. At the same time, blood glucose level will be measured by 5uL of finger prick blood sampling as a baseline glucose level. In an intervention step, we will administer a 75g load of glucose drink or drinking water at each study visit. After then, glucose level testing and EMG/EEG data collection will be performed at 0, 30, 60, 120, and 180 minutes after the drink administration. Once participants complete the first study visit, a study coordinator will schedule their next visit with at least 3-day gap.

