11.1 STATISTICAL ANALYSIS STRATEGIES

Outcome variables include:

Aim 1

- 1) motor-evoked potentials to measure corticospinal excitability (unit: uV)
- 2) TMS-evoked potentials to measure cortical excitability (unit: uV)

Aim 2

- 1) EEG spectral power in the theta-band (4-8Hz) averaged over frontal EEG channels to measure engaged brain network dynamics (unit: dB).
- 2) EEG spectral power in the alpha-band (8-12Hz) averaged over left frontal EEG channels to measure disengaged brain network dynamics (unit: dB).

For all analyses, outcome measures are analyzed as the difference from baseline metrics before the GTT. The repeated measures of primary outcome will be fitted into general linear mixed effect model where baseline measures (continuous), time of measures (categorical), treatment method (binary) and time by treatment as fixed effects, while the within-subject effect among different time point (0, 30, 60, 120, 180 minutes) is modeled as random intercept assuming autoregression model (AR(1)) as covariance structure. The two sided Wald-test of treatment method (fixed effect) between the verum GTT versus control GTT condition is our primary result of interest. We hypothesize a significant main effect for factor GTT but no effect for factor time nor the interaction of GTT by time. We hypothesize that verum-GTT will modulate corticospinal and cortical excitability. In case we do find a significant interaction of GTT by time, we will use post-hoc contrast test to compare the overall differences between verum-GTT versus control-GTT at each time point and correct for multiple comparisons using false discovery rate (FDR) method. All hypothesis tests that are observed to be not statistically significant will be reported as being inconclusive. Based on the nature of our study design, we assume missing data to be minimal, where linear mixed effect model is robust to handle such missing value situations without creating any obvious bias. For all the result tables of statistical analysis, statistical estimates of population parameters will be tabulated along with corresponding confidence intervals (CIs). Given the lack of any comparable study in the literature, we performed a power analysis guided by the number of participants we are able to enroll based on the size of the grant. Briefly, with a sample of N=20 participants, we will be able to detect an effect size of $d_z = 0.66$ with $\alpha = 0.05$ and $\beta = 0.2$. Power analysis was performed with G*Power.

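### The drink may be known before the session 1 baseline is taken, and masked signal processing is not specified for the four outcomes in section 11.1

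*Combined protocol and SAP*

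**What the plan says.** Section 4.1 describes a two-sequence crossover with ten participants per sequence, allocated by "sequentially-numbered opaque sealed envelopes". It states that "the random assignments will be concealed from the personnel who screen potential participants". That protection is stated to last "until the moment that the participant is enrolled and ready for baseline evaluations". It does not say when in the session the envelope is opened, or whether the TMS/EEG operator sees its contents.

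Section 4 lists the steps of each session. Step 3 is "Baseline EEG and MEP measurements elicited by TMS", step 4 is the fasting finger prick, and step 5 is the drink. Section 5.2 defines the resting motor threshold (RMT) as the "minimum TMS intensity required to evoke MEP of at least 50 uV in 50% of 10 consecutive trials". The Study Summary sets the test pulses at 120% of RMT, with 10 pulses at baseline.

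Section 11.1 names four outcomes: MEP, TEP, frontal theta power and left frontal alpha power. For all of them, "outcome measures are analyzed as the difference from baseline metrics before the GTT", and the mixed model also includes the baseline as a covariate.

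On masking, the only wording is in the section 9.1 monitoring plan, where a safety monitor reviews blinded adverse events monthly. Nothing is said about masking the operator, the person who processes the signals or the analyst. No rules are given for MEP trial rejection, EEG artefact handling or TEP windows.

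**The concern.** Envelopes that stay sealed until enrolment guard against selection bias. They do not guard against an operator or data processor who knows the drink and, without meaning to, handles the measurement differently.

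Plain water and a flavoured glucose solution are hard to disguise from the participant. The baseline and the offline processing are therefore the main places where masking remains feasible, and the plan uses neither.

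The plan also has a direction in mind. Section 11.2 frames its precision check around a larger fall in MEP and TEP amplitude with glucose. Section 11.1 expects a treatment main effect without a time effect or an interaction. One baseline per session serves all five post-drink time points, so an error in it moves all five together, which has the same shape as the expected finding.

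**Working it through.** **1. Order of events.** Concealment may end when the participant is ready for baseline evaluations (section 4.1). The operator finds RMT and records baseline MEP and EEG by step 3, and the assignment is first needed at step 5 (section 4). Knowledge is thus allowed at least two steps earlier than it is needed.

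**2. Who would know.** Section 4.1 conceals the sequence from screening personnel. Section 12.4 gives consent, eligibility review, device administration, EEG and data entry to the same roles, and section 5 has one researcher administer all of a participant's assessments. The screener may therefore also be the operator.

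**3. A shifted baseline.** Let Y be the post-drink value, B the same session's baseline, T = 1 for glucose and 0 for water, and b the slope of Y on B.

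- Raw-value model: Y = a + bB + tT.
- Change-score model: Y − B = a + (b − 1)B + tT. The coefficient t is the same, so subtracting the baseline adds nothing once baseline is a covariate.
- If the recorded baseline is B* = B + dT, then Y = a + bB* + (t − bd)T. The bias is −bd. With b between 0 and 1 (an assumption), it lies between 0 and d in size.

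**4. A shifted threshold.** If RMT is found once per session and the intensity is then held, a biased RMT moves baseline and post-drink MEPs together and largely cancels. The documents describe one determination, before baseline, and do not mention repeating it.

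**5. Shifted processing.** If handling moves only the processed post-drink values by e in glucose sessions, the estimate becomes t + e, with no attenuation. If it moves the baseline by d as well, the bias is e − bd. With 10 baseline pulses, each rejected trial is 1/10 = 10% of that block.

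**6. What later opening protects.** There are 20 × 2 = 40 session baselines. In a two-period crossover, anyone who knows the session 1 drink knows the session 2 drink. Later opening therefore protects the 20 session 1 baselines and leaves the 20 session 2 baselines exposed.

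**7. Illustration of size.** The method is a two-sided paired t-test with n = 20, 19 degrees of freedom, alpha 0.05 and noncentrality dz × √20. This is a proxy for the planned Wald test, and the same kind of calculation as the plan's own.

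- The plan's figure first: section 11.1 states dz = 0.66 for 80% power. At dz = 0.66 the power is 0.7995, and the detectable dz is 0.660. The figure reproduces.
- With no true effect and an assumed systematic shift in SD units of the paired difference:

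| Assumed shift (SD) | Noncentrality | Rejection rate |
|---|---|---|
| 0 | 0 | 5.0% |
| 0.1 | 0.447 | 7.1% |
| 0.2 | 0.894 | 13.6% |
| 0.3 | 1.342 | 24.7% |

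Shifts of 0.2 and 0.3 are 0.2/0.66 = 30% and 0.3/0.66 = 45% of the effect the study is sized to detect. The documents give no basis for choosing any row.

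**The case against.** The case on the other side has real force.

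- **The sentence in section 4.1 is about allocation concealment.** It does not say that the operator opens the envelope before baseline. This stands: the plan permits early knowledge and does not require it. A reader might infer that staff do know the drink when they set the intensity, but the documents do not establish that.
- **The documents are silent on processing.** A reader might infer that recordings are processed unmasked. No text says so. What can be said is that masked processing is not provided for and that no processing rules are given.
- **The baseline route is weaker than it looks.** A reader might infer that using the baseline both as the subtracted value and as a covariate doubles its influence. Step 3 shows that it does not: the bias is attenuated by the slope, and a biased RMT largely cancels at constant intensity. Neuronavigation and the numeric threshold rule also limit discretion.
- **Not every measure is exposed.** The trait scales (STAI Y-2, IDAS) are completed at screening, and glucose is read by an analyser. RMT cannot affect theta or alpha if these come from the resting EEG. The concern is confined to the four outcomes in section 11.1.
- **Later opening is only a partial remedy, in a pilot.** This is true, and step 6 quantifies it. It does not reach the second part of the remedy, coded processing, which covers both sessions.
- **The rejection rates restate an assumption.** They do, and they are not evidence that bias will occur.

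**Conclusion.** The point holds in limited form. The stated rule allows the assignment to be known before an operator-taken baseline that enters all four outcomes in section 11.1, and the plan does not provide for masked processing in either session. A baseline shift carries into the treatment estimate in proportion to the slope of post-drink value on baseline. A shift confined to processed post-drink data carries in fully.

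The size of any bias cannot be found from the documents. The 7%, 14% and 25% rejection rates rest on assumed shifts of 0.1, 0.2 and 0.3 SD of the paired difference, no true effect, and a paired t-test at N=20. The baseline result assumes that the covariate is the same session's baseline.

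This is not fatal for a pilot, but it should be changed. The remedy costs little, and a baseline already recorded by someone who knew the drink cannot be repaired. It would be wrong to conclude that later envelope opening removes observer bias: the session 2 drink can still be inferred.

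**What to change.** 1. **Section 4.1.** State that the session 1 envelope is opened only after RMT, baseline MEP/EEG and the baseline finger prick are complete, immediately before the drink. State that this protects session 1 only.
2. **Section 11.1, both sessions.** Fix the rules for MEP trial rejection, EEG artefact handling and TEP and peak measurement before processing begins. Store recordings under codes that hide the drink. Complete MEP, TEP and spectral processing for both sessions before codes are linked to drink.

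**Cost.** A change to when an envelope is opened, plus minor file handling. No extra participants, visits or staff are needed: the codes can be generated by a short program or held by an existing team member. The glucose solution comes ready bottled (section 11.3), so later opening should not delay the session.

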5 STUDY SCHEDULE

In order to increase data quality, the assessments for an individual participant will be administered by the same researcher. It is important to note that consent, scales, and experiments will all take place in a private room. Any phone calls will take place in a private lab environment as well.

5.1 SCREENING

- Phone screening

The phone screening allows researchers to screen out participants based on self-report responses and for potential participants to become familiar with the study schedule, including procedures. During the telephone screening, researchers will provide a brief background about GTT, TMS, and EEG. The timeline will be explained to the participants and the participant will be informed of compensation, both amount and payment schedule. The participant will be asked if they have any questions. Once all questions have been answered, the participant will be asked if he/she is still interested in participating in the study. If yes, the researcher will ask if the participant will provide verbal consent to begin the initial phone screening which will determine eligibility for the stimulation session. A telephone script, which includes the screening questions, is provided in *Appendix E*.

- Screening visit (Visit 1)

Participants who pass an initial screening by a telephone call are asked to attend a screening visit where consent is provided, eligibility for study participation is confirmed and demographic information is collected. To ensure that all aspects of the research are understood, participants may be asked a series of questions about the research they are about to take part in (*Appendix C*). After then, participants are asked to provide weight and height for calculating body mass index (cut-off level < 30). Fasting blood sugar test level will be collected (cut-off level < 95 mg/dL). If participants meet the inclusion/exclusion criteria, they will be asked to visit 2 study sessions after an MRI scan. Also, participants will perform a cognitive control task to measure baseline cognitive function. At the screening session, the participants will complete the STAI form Y-2 and the IDAS to determine their trait levels of anxiety and depression. This data will be used to explore how a participant's trait levels of anxiety and depression affect their corticospinal activity. The BIS/BAS and STAI form Y-1 questionnaires will be administered twice at each experimental session, once before the drink administration and once three hours after. The PANAS questionnaire will be administered before the drink administration, as well as 0, 30, 60, 120, and 180 minutes after the drink administration. The scores on these questionnaires will be compared before and after the drink administration to determine how the drink affected the participants' psychological state over time. For each participant, scores on these questionnaires will be compared between the session during which they consumed glucose and the session during which they consumed water.

- Questionnaires (*Appendix F*)

Participants will be asked to complete the following questionnaires.

1. State-Trait Anxiety Inventory (STAI): a 40-item self-report questionnaire for assessing state and trait anxiety). This questionnaire will be used to determine each participant's level of both state and trait anxiety
2. The Positive and Negative Affect Schedule (PANAS): a self-report questionnaire that consists of two 10-item

scales to measure both positive and negative affect. This questionnaire will be used to measure participants' positive and negative effect.

3. The Edinburgh Handedness Inventory: a well-known questionnaire for determining objectively whether one is left or right handed. This will be used to confirm that all participants are right-handed.

4. Behavioral avoidance/inhibition (BIS/BAS) scales: a questionnaire that consists of 24-item for assessing behavioral inhibition, behavioral activation, and affective responses to impending reward and punishment. This questionnaire measures each participant's motivation to avoid adverse events and approach goal-directed activity. Since a loss of motivation is a key element of depression and other psychological illnesses, this questionnaire can indicate psychological well-being.

5. Inventory of Depression and Anxiety Symptoms (IDAS): a questionnaire that consists of 64 items to assess specific symptom dimensions of major depression and related anxiety disorders. The IDAS consists of ten symptom scales including suicidality, lassitude, insomnia, appetite loss, appetite gain, ill temper, well-being, panic, social anxiety, and traumatic intrusions.

5.2 STUDY SESSIONS

- MRI scan (Visit 2)

We will ask participants to come in and complete an MRI scan. MRI scan imaging will take place at the Biomedical Research Imaging Center (BRIC), located on the first floor in Marsico Hall. Screening questions will be completed prior to the MRI scan (attached) and all preparations for the scan will take place in a facility area behind a locked door, where only research study personnel have access. When subjects are required to change their clothing, they will be allowed to do so alone, in a room with a door that locks. MRI scan will be performed by trained study personnel or designees of the PI that are approved to complete an MRI scan.

- Study sessions (Visit 3-4)

All participants will undergo two study sessions (glucose or water administration) with at least 3-day gap to minimize the effect of either GTT or TMS. In each visit, all participants will be asked to fill out the questionnaires at the beginning and end of the session. Participants undergo a two-minute eyes-open resting-state EEG recorded with high-density, 128 channels EEG system (Netamps 410, Electrical Geodesics Inc, EGI) using Geodesic Sensor Nets (sampled at 1000 Hz). EEG nets will be fitted at the beginning of the two study visits and remain in place until completion of the study visit. Also, participants will perform a cognitive control task to investigate if changes in glucose blood level could modulate cognition.

Single-pulse TMS on the motor cortex leads to a twitch in the target muscle evoking a motor-evoked potential (MEP) measured by electromyography (EMG) electrodes. Participants will be seated in a comfortable armchair with their hands positioned on the armrest. Two disposable electrodes (15x21mm, Ambu Neuroline) will be placed in a tendon-belly arrangement over the first dorsal interosseous muscle and a ground electrode will be placed over the styloid process of the ulna. A figure-eight coil (C-B60, MagVenture) will be used for stimulation and EMG signals will be recorded by an amplifier (MagPro X100, MagVenture). The coil will be placed tangentially over the scalp with the handle pointing backwards and laterally at 45° from the mid-sagittal line. Biphasic TMS pulses will be applied over the motor cortex and the resting motor threshold (RMT) will be defined by the minimum TMS intensity required to evoke MEP of at least 50 uV in 50% of 10 consecutive trials. At baseline, 10 TMS pulses will be applied on the scalp and EEG and EMG data will be collected. At the same time, blood glucose level will be measured by 5uL of finger prick blood sampling as a baseline glucose level. In an intervention step, we will administer a 75g load of glucose drink or drinking water at each study visit. After then, glucose level testing and EMG/EEG data collection will be performed at 0, 30, 60, 120, and 180 minutes after the drink administration. Once participants complete the first study visit, a study coordinator will schedule their next visit with at least 3-day gap.

6 STUDY PROCEDURES/EVALUATIONS

6.1 SELF-REPORT MEASURES

Study coordinators will consider using a standard safety questionnaire to screen TMS candidates. The following questions represent the basic information required. Additional information may change according to particular demands. Consensus has been reached for this questionnaire (Rossi et al., 2009).

1. Did you ever have a concussion?
2. Do you have or have you ever had diabetes?
3. Do you have or have you ever had anorexia?
4. Do you have or have you ever had OCD?
5. Do you have or have you ever had ADHD?
6. Have you ever had a fainting spell or syncope? If yes, please describe in which occasion(s)
7. Have you ever had severe (i.e., followed by loss of consciousness) head trauma?
8. Do you have any hearing problems or ringing in your ears?
9. Are you pregnant or is there any chance that you might be?
10. Do you have metal in the brain/skull (except titanium)? (e.g., splinters, fragments, clips, etc.)
11. Do you have cochlear implants?
12. Do you have an implanted neurostimulator? (e.g., DBS, epidural/subdural, VNS)
13. Do you have a cardiac pacemaker or intracardiac lines or metal in your body?
14. Do you have a medication infusion device?
15. Are you taking any medications? (Please list)
16. Did you ever have a surgical procedures to your spinal cord?
17. Do you have any disorder related to spinal cord or ventricle?
18. Did you ever undergo TMS in the past?

We will ask these questions in order to follow the standard safety guidelines for TMS studies. Answers from the questions will help us to exclude study participants regarding the safety of TMS

